5.3. Prohibited Medications and Restrictions

- Allopurinol and other urate lowering agents (e.g., probenecid, rasburicase) for the treatment of gout. Patients treated with uric acid lowering agents for elevated uric acid levels with no history of gout can, with the agreement of their treating physician, undergo a 2 month washout of uric acid lowering medication and then be tested to determine if uric acid entry criteria are met.
- Herbal supplements that may have urate lowering actions (e.g., Devil's Claw or Harpagophytum procumbens, Indigenous cinnamon or Cinnamomum osmophloeum, Skunkvine or Paederia scandens or Paederia foetida)
- Azathioprine
- 6-Mercaptopurine
- Didanosine
- Warfarin
- Tamoxifen
- Amoxicillin/ampicillin
- Any other drug for which there is evidence of interaction with allopurinol
- Dual RASB therapy (i.e., another RASB medication in addition to that already in use)
- Non-RASB antihypertensives that are not listed in the PERL approved menu of antihypertensive drugs, unless these were in use before joining the study.

5.4. Randomization Procedures

After the run-in period (described in Section 8.3) and with a valid baseline iohexol GFR measurement prior to randomization, participants will be randomized in a 1 to 1 ratio to receive either oral allopurinol or placebo. Randomization will be stratified by center, uric acid (≤ 6.0 vs. > 6.0 mg/dl), and HbA1c (≤ 7.8 vs. $> 7.8\%$). Randomization will be performed using permuted blocks, with a block size that is known only to the DCC. After a participant has been randomized, the clinical site will send a study medication request to the research pharmacy, including the participant's address, so that the study medication can be directly mailed to the participant. Clinical sites will not have access to the treatment

assignment (see 6.2., Blinding Procedures). This will be directly communicated or made electronically available to the pharmacy by the DCC.

5.5. Discontinuation of study drug

5.5.1. Reasons for discontinuation

The study drug will be *temporarily* discontinued if a participant:

- Has clinically significant persistent changes from baseline based on laboratory safety assessment results (the response to discontinuation will be monitored to assess whether the drug can be re-instituted, see next paragraph on permanent discontinuations).
- Requires treatment with allopurinol or medications that make allopurinol contraindicated (see 5.5.2 and 9.5).
- Becomes pregnant or breastfeeding (see 5.5.2)

Whenever the reason for temporary discontinuation of the study drug ceases to exist, the study medication will be resumed with the consensus of the drug monitoring committee, according to the following procedures:

- If the study medication was discontinued because of a suspected drug reaction or the participant was off-medication for 3 months or longer, the study drug will be re-started at a dosage of 100 mg for 4 weeks, which will then be increased to the full dosage appropriate for the eGFR. (see 6.1.2)
- If the study medication was not discontinued because of a drug reaction and the participant was off-medication for less than 3 months, the study medication will be re-started, at the full dosage appropriate for the eGFR.

The study drug will be *permanently* discontinued if a participant:

- Experiences an SAE related to the study drug or an intolerable AE such as a persistent allergy or rash.
- Has clinically significant persistent changes from baseline based on laboratory safety assessment results which do not respond to temporary 2-week discontinuation of study drug and re-institution of drug at ½ of the initial dose.
- Develops end-stage renal disease (confirmed eGFR ≤ 15 ml/min/1.73 m² in the absence of acute kidney injury [AKI], institution of chronic dialysis treatment or kidney transplantation) or iGFR decreases by 50% from one measurement to the next or serum creatinine levels double over any 12 month interval in the post-randomization period. If any of these renal function changes prove to be temporary, the study medication could be resumed as described above with the consensus of the drug monitoring committee.

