9. SAFETY ASSESSMENTS

9.1. Demographic Data/Medical History

After collecting a detailed medical history at Visit 1, this information will be updated at each visit through a structured interview, with a special emphasis on skin symptoms and signs such as rash, itching and exfoliation and on pregnancy in females. Participants will be instructed to communicate any change in their health status and intervening hospitalizations to the study coordinator in-between visits. In particular, they will be instructed to discontinue study medication and immediately contact the study coordinator if they develop a suspicious skin rash, swelling of the lips or mouth, arthralgias, and/or jaundice, which may indicate a hypersensitivity reaction to allopurinol. Fever and chills should also be reported but would not require cessation of medication prior to discussion with study personnel.

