13.4.2. Risks associated with allopurinol treatment

Allopurinol has been used for several decades for the long-term therapy of symptomatic gout. The risks associated with its use are low and include:

- a. Skin rashes, usually pruritic maculopapular skin eruptions, sometimes scaly or exfoliative, are the most commonly reported adverse effect of allopurinol. Skin reactions were observed in the past in up to 3% of treated patients, but more recent data suggest that their frequency is now less than 1% (www.drugs.com/pro/allopurinol.html) perhaps more likely due to changes in the filler compounds rather than the actual drug. Rashes may be followed by more severe hypersensitivity reactions such as exfoliative lesions and the Stevens-Johnson syndrome (erythema multiforme major), which can be fatal. Although such occurrence is very rare, in the order of 1 in 10,000⁴⁸, treatment with allopurinol will be immediately discontinued if a rash develops and will not be reinstated. As noted, those with HLA-based genetic susceptibility to allopurinol-related SJS will be screened out. About 0.7% of Whites and 2-3% of African Americans and Asians are carriers of such genetic susceptibility.
- b. An increased frequency of acute gout attacks has been reported during the early stages of allopurinol administration, possibly resulting from the mobilization of urates from tissue deposits causing fluctuations in serum UA levels. Early studies estimated the risk of such events to be about 6%, but an analysis of current usage suggests that the risk has now decreased to less than 1% (www.drugs.com/pro/allopurinol.html). The risk is expected to be even lower in this study population since individuals with a previous history of gout will be excluded and UA levels will be on average lower than in patients usually taking allopurinol for elevated UA levels.
- c. Reversible liver damage as well as asymptomatic rises in liver enzymes has been observed in 1-2% of patients taking allopurinol. Some very rare cases of irreversible liver damage have been observed in the context of the Stevens-Johnson syndrome.
- d. Bone marrow depression has been reported in patients receiving allopurinol, most of whom received concomitant drugs with the potential for causing this reaction. Bone marrow depression has been rarely observed in patients receiving allopurinol alone.

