13.5. Procedures for protecting against and minimizing potential risks

a. General

The patients are under constant medical supervision. They are told that the data which are collected will be used for scientific report, but they will not be identified in such reports.

b. Specific

1. Regular pregnancy tests and education regarding fetal risk of the study drug will be provided to female patients of child bearing age.
2. Quarterly measures of liver enzyme and white blood cell count will allow for early detection of liver injury or leucopenia potentially representing drug toxicity.
3. Quarterly measures of serum creatinine will allow titration of allopurinol in relation to kidney function to avoid excessive dosage of the medication.
4. IV's for kidney function studies will be placed by trained skilled clinical research nurses or technicians or by experienced physicians.
5. Blood drawing for laboratory studies will be performed by trained skilled phlebotomy personnel at the respective institutions, thus limiting the risk of discomfort or local hematoma formation.
6. Participants will be advised not to donate blood throughout the time they are in the study.
7. Regarding possible drug toxicity:
 - a. To avoid fetal risks from the study drug, patients planning pregnancies will not be included. Sexually active female patients will be instructed to immediately discontinue study drugs and RAS blockers if a menstrual period is missed by more than two weeks and, if found to be pregnant, the study medication and RAS blocker will be discontinued and not resumed until pregnancy and nursing are completed. Pregnancy tests will be done on all women of child-bearing potential at each visit.
 - b. Subjects with known allergy to xanthine-oxidase inhibitors will be excluded from the study. Patients will be instructed to immediately report skin reactions and allergic symptoms and to immediately stop the study medication should these occur. Patients will be given antihistamines for symptom relief. A small supply of antihistamines to be used in such an event will be supplied to each patient. Should an allergic reaction or skin rash occur, the study drug will be permanently discontinued.

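### Protocol 5.5.1, read alone, could support restarting study drug after a transient, tolerable, non-serious rash or allergic reaction, which 13.4.2.a and 13.5.b.7.b do not allow

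*Protocol*

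**What the plan says.** Section 13 of the current protocol treats any rash as the end of study drug. Under 13.4.2.a, "treatment with allopurinol will be immediately discontinued if a rash develops and will not be reinstated". Under 13.5.b.7.b, "Should an allergic reaction or skin rash occur, the study drug will be permanently discontinued". Neither sentence is limited by severity, duration, tolerability or cause.

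Section 5.5.1, which sets out the reasons for stopping, is narrower. Among its permanent-stop reasons is that the participant "Experiences an SAE related to the study drug or an intolerable AE such as a persistent allergy or rash". Its restart procedures apply "Whenever the reason for temporary discontinuation of the study drug ceases to exist", and they need the consensus of the Drug Monitoring Committee. One of them begins "If the study medication was discontinued because of a suspected drug reaction or the participant was off-medication for 3 months or longer" and leads to 100 mg for 4 weeks, followed by the full eGFR-based dose. It makes no exception for rash or allergy and does not refer to section 13.

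The instructions to participants differ in a similar way. Section 9.1 tells them to stop study drug and "immediately contact the study coordinator if they develop a suspicious skin rash". Section 13.5.b.7.b is wider: "Patients will be instructed to immediately report skin reactions and allergic symptoms and to immediately stop the study medication should these occur".

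**The concern.** Rash is described in 13.4.2.a as the most commonly reported adverse effect of allopurinol. The same paragraph ties the no-reinstatement rule to possible progression to severe hypersensitivity, including Stevens-Johnson syndrome. Re-exposure after a rash is therefore the step that section 13 is written to prevent.

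A committee member who turns to 5.5.1 for the stopping rule finds that the permanent stop is tied to *intolerable* and *persistent* reactions, and that there is a restart schedule after a suspected drug reaction. For a mild rash that clears quickly, that member could reasonably conclude that a restart is open. A member who turns to section 13 would conclude that it is not.

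The answer also decides whether such a participant is counted among permanent discontinuations because of adverse effects, a safety outcome in SAP 6.8.2.

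**Working it through.** No power or sample-size figure is involved. The check sets the sections side by side for each kind of reaction and then sizes the group.

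**Case by case**

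- *Drug-related serious reaction.* 5.5.1: permanent stop. Section 13: permanent stop if it is a rash or allergic reaction. No conflict.
- *Intolerable or persistent non-serious rash.* 5.5.1: permanent stop. 13.4.2.a and 13.5.b.7.b: permanent stop. No conflict.
- *Transient, tolerable, non-serious rash.* 13.4.2.a: stop and do not reinstate. 13.5.b.7.b: permanent stop. 5.5.1: its permanent-stop reason is not clearly met, and its restart bullet does not exclude the case. The sections can give different answers.
- *Transient, tolerable, non-serious allergic reaction without rash.* 13.5.b.7.b: permanent stop. 13.4.2.a does not address it. 5.5.1: as in the previous case. The sections can give different answers, and the prohibition rests on 13.5.b.7.b alone.

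Section 9.2 requires an immediate stop for suspected drug allergy but is silent on restart, so it does not settle the last two cases.

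**Size**

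Inputs: 480 participants planned (Protocol section 3) and 530 in the SAP overview, randomized 1:1. For skin reactions, 13.4.2.a gives a historical rate of up to 3% and adds that "more recent data suggest that their frequency is now less than 1" percent.

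- Arm size: 480 / 2 = 240; 530 / 2 = 265.
- At 1%: 240 × 0.01 = 2.4; 265 × 0.01 = 2.65. Since the rate is below 1%, this means fewer than 3.
- At 3%: 240 × 0.03 = 7.2; 265 × 0.03 = 7.95. This means about 8.

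These counts describe skin reactions reported as an effect of the drug. The documents do not say what share is transient and tolerable. They also give no rate for rashes from other causes, which the unqualified section 13 rule covers in both blinded arms. The counts are an order of magnitude and not a limit.

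**The case against.** The strongest reply is that 5.5.1 in context opens no restart route for rash. Its restart bullets sit under temporary discontinuation, and the three temporary reasons are laboratory changes, a need for allopurinol or a contraindicating drug, and pregnancy or breastfeeding. Rash and allergy are absent. The restart cases worked out elsewhere are white-cell count and liver enzymes (13.5.b.7.f and h), which fit a suspected drug reaction well. Stopping permanently obeys every section. This stands, and it rules out two inferences a reader might draw: that the sections cannot be reconciled, and that 5.5.1 directs a restart after rash. What remains is that the ordinary meaning of a suspected drug reaction includes rash, and the bullet does not say otherwise.

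A second reply is that the qualifiers in 5.5.1 have other work to do. *Intolerable* is needed for adverse events other than rash, and *persistent* may attach to allergy only. That is fair, but on this reading rash still appears as an example of an intolerable event, so a tolerable rash is still not named.

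Third, wrongful re-exposure is unlikely. Section 5.5.2 sends site-decided stops to the Drug Monitoring Committee within 10 days, restart needs its consensus, and 9.2 requires dermatologic consultation when drug allergy is suspected. This stands and limits the severity. It does not tell the committee which rule to apply.

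A reader might also infer that nothing in the protocol settles precedence between the sections. That is too absolute. Section 14 refers to section 15.1 in connection with committee action on study medication, and the current 15.1 was not in the text available for this review.

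**Conclusion.** The point holds as a minor internal inconsistency in safety wording. It is confined to transient, tolerable, non-serious rashes and allergic reactions. For these, section 13 requires a permanent stop, while 5.5.1 read alone could support a committee-approved restart.

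At the quoted rates, drug-attributable rashes in the allopurinol arm would run from fewer than 3 to about 8. It is tempting to read those as ceilings on the number affected. The documents do not support that, because the section 13 rule has no attribution limit and applies in both arms; nor do they show that the number is above zero. Each participant whose handling changes moves the permanent-discontinuation count in SAP 6.8.2 by one. The primary intention-to-treat analysis is not materially affected, since participants are analysed as randomized whether or not they stay on drug.

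The conclusion assumes that the current section 15.1 contains no rule on rash or on precedence between sections.

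**What to change.** Make two changes in 5.5.1:

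1. Bring the permanent-stop bullet into line with 13.5.b.7.b, so that a skin rash or allergic reaction is a permanent stop in its own right, alongside drug-related SAEs and other intolerable adverse events.
2. Limit the restart bullet to a suspected drug reaction *other than a skin rash or allergic reaction*.

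The sponsor may prefer that a clearly unrelated rash should not end study drug. The list of protocol changes shows that 9.1 was deliberately narrowed to a *suspicious* rash, so this may be the intent. In that case, add one attribution qualifier, for example *suspected to be drug-related*, and use it identically in 5.5.1, 9.1, 13.4.2.a and 13.5.b.7.b.

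The cost is a wording amendment and a memo to sites, pharmacy and the Drug Monitoring Committee. The downside is that a few participants with mild rashes lose study drug, as section 13 already requires. Sample size and the primary analysis do not change.

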5.5.2. Handling of study drug discontinuation

- Date and reason for drug discontinuation will be recorded on the relevant Case Report Form.
- All study discontinuations decided by a clinical site will have to be reviewed and approved by the Drug Monitoring Committee within 10 days from their start.
- If the study drug is discontinued due to treatment with medications that make allopurinol contraindicated (e.g. amoxicillin/ampicillin) or due to pregnancy/breastfeeding, the possibility of resuming the study drug will be evaluated by the Drug Monitoring Committee once those medications have been discontinued or pregnancy/breastfeeding has ended.

- If the study drug is temporarily discontinued and then re-instated, the end-date of the intervention will remain the same as if the study drug had not been discontinued. All visits will be carried out as scheduled while the study drug is temporarily discontinued.
- Unless a participant withdraws consent all participants that are permanently discontinued from study drug or who discontinue study medication on their own will be followed for the full study period (i.e., 164 weeks, including the washout period) and all data will be collected as scheduled.
- If a participant reaches ESRD as defined above under 5.5.1,, he/she will be permanently discontinued from the study and invited to participate in a study close-out call or visit to be held within three months from the occurrence of ESRD. Data collection at this call or visit will be limited to standard adverse event reporting. In addition, sites should continue to contact participants who have reached end-stage renal disease to determine their final status until 3 years and 2 months after randomization. Major attempts will be made to schedule an end-of-study assessment for all participants who are lost to follow-up during the course of the study.

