7.2. Secondary outcomes

1. Iohexol-clearance GFR at the end of the 3-year treatment period (before the washout).
2. Iohexol-clearance GFR time trajectory estimated from periodical iohexol-GFR measurements.
3. Estimated (eGFR) at 4 months estimated from serum creatinine and cystatin C and adjusted for the eGFR at baseline.
4. Estimated GFR (eGFR) time trajectory estimated from quarterly serum creatinine and cystatin C measurements using the CKD-EPI SCr and the CKD-EPI SCr-SCysC equations.^{34,35}
5. Time to doubling of baseline serum creatinine value or ESRD (eGFR ≤ 15 ml/min/1.73 m², institution of dialysis, kidney transplantation).
6. Geometric mean of two AER measurements at the end of the 2-month wash-out period following the 3-year treatment period, adjusted for the mean urinary AER at baseline. Urinary

AER will be determined in timed overnight urine collections brought by study participants to regular clinic visits, and expressed in $\mu\text{g}/\text{minute}$ and as urinary albumin/creatinine ratios.

7. Geometric mean of urinary AER during the last three months of the treatment period (Visits 15 and 16), adjusted for the mean urinary AER at baseline.
8. Time to fatal or non-fatal cardiovascular events, defined as the composite of CVD death (ICD-10 code I10 to I74.9), myocardial infarction, stroke (ischemic or hemorrhagic), coronary artery bypass grafting, or percutaneous coronary intervention.

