8.5. Treatment Period (Visits 6 to 15)

During the treatment period, the following procedures will be completed at each visit for each participant:

- Obtain interval medical history (with special emphasis on BP control and CVD events).
- Review of concomitant medications and AEs.
- Review RASB and BP therapy.
- Measure height, weight, and vital signs according to the schedule outlined in Figure 1
- Inspect for skin rash.
- Conduct a physical exam (Visit 11).
- Perform ECG according to the schedule outlined in Figure 1 (Visit 11).
- Collect samples for clinical laboratory assessments and for storage of serum, plasma and urine for later biomarker research according to the schedule outlined in Figure 1.
- Perform pregnancy test in women of childbearing potential.
- Measure GFR by means of plasma disappearance of non-radioactive iohexol, iGFR at Visit 11.
- Provide a container and instructions for an overnight urine collection whenever an AER measurement is scheduled at the following visit.

In the days immediately after each visit, upon completion of serum creatinine measurements, participants will receive a new batch of study medication by mail from the research pharmacy. Upon receipt of the new tablets, participants will be instructed to immediately mail the pill bottles or the blister packs with the tablets remaining from the previous prescription to the study center for drug accounting and compliance assessment (see 6.1.2). A pre-stamped and addressed envelope will be provided to participants for this purpose.

At some sites the study medication may be dispensed directly to the study participant at a relevant in person study visit or by mail from the site following a relevant in-person or phone study visit.

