8.10. Early Withdrawal

Unless the participant withdraws consent, all randomized participants will be followed for the full study period (through week 164) and all data will be collected as scheduled.

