3.8. Modifying definition of per-protocol analysis set

RATIONALE:

Following internal discussion we modified the per-protocol definition as follows.

PROTOCOL:

- **Per Protocol:** ... The per protocol population will exclude subjects ... as well as data points for which the cumulative exposure to the study medication from

randomization to that time point was less than 80% of the theoretical full exposure (see Section 11.1 in the protocol).

SAP:

- **Per Protocol:** ... The per protocol population will exclude subjects ... for whom the average drug exposure was less than 80% (see Section 11.1 in the protocol).

4. Study Aim

The study aim is to determine whether lowering serum UA by means of oral allopurinol is effective in preventing or slowing decline of renal function in T1D patients with history and/or presence of microalbuminuria or moderate macroalbuminuria, or with ongoing GFR loss regardless of history or presence of albuminuria, who have only mildly or moderately impaired kidney function.

5. Study Estimands

This section describes the primary and secondary estimands for corresponding endpoints and variables of interest. We follow ICH-E9 (R1) recommendations and specify estimands in terms of four attributes defining the treatment effect of interest:

- A1. The target population
- A2. The variable (or endpoint) to be obtained for each patient that is required to address scientific question of interest
- A3. Strategies for addressing intercurrent events
- A4. The population summary for the variable (endpoint), that provides a basis for a comparison between treatment conditions.

In Table 5.1. we include various intercurrent events that occurred in the PERL study and divide them into three groups, based on their implications for subsequent data collection of the endpoint of interest.

Table 5.1. Groups of intercurrent (IC) events in PERL study

Group of IC events	IC event	Implications for Post-IC data
Group A	Non-adherence to study drug schedule	Post-IC data are collected, but their interpretation may be affected depending on the estimand of interest
	Permanent discontinuation of study drug	
	Use of prohibited medication	
	Missed scheduled visit	
Group B	ESRD treatment (hemodialysis or transplant for ESRD subjects)	Post-IC data do not contain any relevant information about estimands of interest and for this reason they are not collected
Group C	Early discontinuation from the study	Post-IC data cannot be collected
	Terminal event, i.e. death	

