5.2.8. Estimand for the time to fatal or non-fatal cardiovascular events endpoint

This is de-facto (effectiveness) estimand for fatal and non-fatal cardio-vascular events with the following attributes:

A1. Target population: Individuals with T1D meeting the inclusion/exclusion criteria specified in the Study Protocol.

A2. Variable of interest (endpoint): This secondary endpoint is defined as a composite of multiple events: (1) Cardiovascular disease (CVD) death (ICD-10 code I10 to I74.9), (2) Myocardial infarction, (3) Stroke (ischemic or hemorrhagic), (4) Coronary artery bypass grafting, or (5) Percutaneous coronary intervention. Time to fatal or non-fatal cardiovascular events is defined as the time from randomization to the first event (one of the events defined above) or censoring (lost-to-follow-up, withdrawal, non-CVD death, and study completion without experiencing the event).

A3. Strategies for different groups of IC events: Depending on IC event group membership (see Table 5.1) variable of interest/endpoint values, collected after IC event in

- Group A will be considered as directly interpretable. Effectively IC events in this group are ignored, which is consistent with ITT principle.
- Groups B and C (except CVD death) are assumed to conform a hypothetical scenario in which variable of interest/endpoint values have similar distribution to subjects not experiencing IC event.

A4. Population summary to compare treatments: Hazard ratio for allopurinol versus placebo

6. Analytical Strategy

In the initial analysis of the primary outcome we will present iGFR univariate statistics by Treatment Groups at each study visit (V4, V11, V16 and V17).

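### After ESRD, no part of the plan requires non-fatal cardiovascular events or cause of death to be recorded, and the SAP's handling of the cardiovascular endpoint does not make up for it

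*Protocol*

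**What the plan says.** Protocol 7.2, outcome 8, is "Time to fatal or non-fatal cardiovascular events, defined as the composite of CVD death (ICD-10 code I10 to I74.9), myocardial infarction", stroke, CABG or PCI. During treatment these events come mainly from the interval history at scheduled visits, which Protocol 8.5 directs towards CVD events.

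Protocol 5.5.1 defines ESRD as a confirmed eGFR of 15 ml/min/1.73 m² or lower "in the absence of acute kidney injury [AKI], institution of chronic dialysis treatment or kidney transplantation". These are three alternative routes. Under 5.5.2, a participant who meets any of them is not only taken off study drug: "he/she will be permanently discontinued from the study and invited to participate in a study close-out call or visit", within three months. Of that contact it says "Data collection at this call or visit will be limited to standard adverse event reporting". Sites are then to keep contacting the participant for 'final status' until 3 years 2 months after randomization. The term is not defined.

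Protocol 8.10 says that, short of withdrawn consent, "all randomized participants will be followed for the full study period (through week 164) and all data will be collected as scheduled". It makes no exception for ESRD.

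SAP Table 5.1 places dialysis or transplant for ESRD in intercurrent-event Group B and says "Post-IC data do not contain any relevant information about estimands of interest and for this reason they are not collected". For the cardiovascular endpoint, SAP 5.2.8 labels the estimand de-facto, and "Groups B and C (except CVD death) are assumed to conform a hypothetical scenario" in which outcomes resemble those of subjects without the event. Its censoring list is loss to follow-up, withdrawal, non-CVD death and completion. SAP 6.7.8 specifies a single Cox model.

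**The concern.** Required ascertainment of part of a prespecified secondary endpoint ends on a post-randomization renal outcome that the treatment is meant to change. SAP 6 tests that endpoint at 0.05. The reason given in Table 5.1 can be argued for GFR, where dialysis or transplant makes the measurement uninterpretable. It cannot be carried over to cardiovascular events: an MI after dialysis starts is an event of interest.

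If cardiovascular risk rises after ESRD, leaving the risk set at ESRD is informative, and the arm with more ESRD has its event rate understated. If deaths are learned through 'final status' but non-fatal events are not, the components of one composite are observed for different lengths of time.

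**Working it through.** **The passages side by side**

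1. *Collection.* Up to ESRD, events come from the scheduled interval history and from adverse event reporting. Up to close-out, only adverse event reporting remains. After close-out, only 'final status' remains. No section ties that term to the outcome-8 components, their dates or cause of death.
2. *Follow-up rule.* 5.5.2 and 8.10 cannot both be followed for a participant with ESRD.
3. *Group B against the ESRD definition.* Group B names dialysis and transplant; Protocol 5.5.1 also includes ESRD by eGFR alone. Those participants have no explicit strategy. They might be put in Group C (early discontinuation), but Table 5.1 describes Group C data as impossible to collect, and here the site is still in contact.
4. *Censoring date.* SAP 5.2.8 does not list ESRD. Protocol 11.4 item 7 applies the rule of item 4, censoring at the last study visit. If the participant is censored at the last visit, censoring is informative whenever risk changes at ESRD. If event-free time runs to the last 'final status' contact, person-time is counted while non-fatal events may go unobserved. The SAP does not choose.
5. *Sensitivity.* The tipping-point analysis in SAP 6.6.1 covers the primary estimand only. SAP 6.7.8 has none.

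**Size, as an illustration**

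The plan gives no event count or power for this endpoint, so there is no figure to reproduce. From the documents: N = 530 (SAP 1) and 164 weeks = 164/52.18 = 3.143 years. Assumed: ESRD proportion e of 1% to 5%, onset spread evenly over follow-up; cardiovascular rate r of 1% to 2% per year before ESRD; rate ratio k of 1 to 10 afterwards; no event recorded after ESRD.

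- Total person-years: 530 × 3.143 = 1,666.
- Person-years after ESRD, P = 530 × e × 3.143/2. For e = 1%: 5.3 × 1.571 = 8.3 (0.5% of the total). For e = 5%: 26.5 × 1.571 = 41.6 (2.5%).
- Share of events missed = kP / [(1,666 − P) + kP]; r cancels.
- Example, e = 5%, k = 5: 208.2 / (1,624.2 + 208.2) = 11.4%.

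| Rate ratio k | ESRD 1% | ESRD 5% |
|---|---|---|
| 1 | 0.5% | 2.5% |
| 3 | 1.5% | 7.1% |
| 5 | 2.5% | 11.4% |
| 10 | 4.8% | 20.4% |

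If adverse event reporting captures everything for the first three months after ESRD, the k = 5 row falls to 2.1% and 9.6%. The number missed is P × r × k: from 8.3 × 0.01 × 1 = 0.08 to 41.6 × 0.02 × 5 = 4.2 for k up to 5, and about 8.3 at the extreme of k = 10. About 16 to 33 events would be observed.

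**The case against.** A reader might infer that cardiovascular events are not measured at all after ESRD. The documents do not support that. Contact continues to 3 years 2 months, and death is plausibly part of 'final status'. SAP 5.2.8 excepts CVD death from the hypothetical scenario, although the exception may attach only to Group C. Up to close-out, an MI, stroke or revascularization would be reportable as an adverse event, and usually as a serious one (Protocol 10.1 and 14). The Manual of Operations and the case report forms might ask for more. What stands is that later collection is not specified.

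A reader might also infer that the SAP names ESRD as a censoring event. It does not; that is part of the ambiguity.

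On 8.10, 5.5.2 can be read as the specific exception to a general rule. The list of changes shows that the ESRD provision was added deliberately in the February 2018 version. That makes 8.10 an unharmonised sentence, but current text should not leave a site to work this out.

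The illustration leans high. Before the 2018 version, participants with ESRD were included in full follow-up, yet the calculation applies the loss to the whole trial. Entry eGFR is generally 40 or more and assumed loss is 3 ml/min/1.73 m² per year, so ESRD should be uncommon and tend to come late. The endpoint counts first events only, and some deaths would be found. The comparison is also imprecise in any case: with 17 to 33 events, the 95% interval for the hazard ratio spans about exp(1.96 × 2/√33) = 2.0 to exp(1.96 × 2/√17) = 2.6 either way. All of this lowers the stakes; none of it supplies the missing rule.

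Finally, a hypothetical strategy is a legitimate choice, and the SAP version that introduced it was approved by the Steering Committee, NIDDK and the DSMB. It still does not fit the de-facto label, and it is untested for this endpoint.

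**Conclusion.** The point holds as a gap in required ascertainment and in the SAP's handling of one secondary endpoint. Followed as written, the plan does not require non-fatal cardiovascular events or cause of death to be recorded after close-out. Its stated reason does not apply to this endpoint, and the analysis rests on an untested assumption of non-informative censoring.

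The size is unknown. On assumed rates it runs from negligible to perhaps 10% of events, and reaches 20% only with a tenfold rate and 5% ESRD together. Elevated cardiovascular risk after ESRD is plausible, but it is an assumption here, since the documents give no such rate.

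A reader might infer a definite bias towards no benefit. That would need both a higher rate after ESRD and more ESRD on placebo. With the opposite imbalance the bias reverses; with equal ESRD and equal risk after it in both arms, the loss is mainly one of precision. The primary iGFR endpoint is not affected by this gap, because SAP 6.5 imputes post-ESRD values.

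**What to change.** - **Protocol 5.5.2:** define 'final status' so that the existing contacts to 3 years 2 months record vital status, cause of death, and each outcome-8 component with its date.
- **Protocol 8.10:** cross-reference 5.5.2, so that the two sections give one follow-up rule.
- **SAP Table 5.1 and 5.2.8:** state that ESRD, whether by eGFR, dialysis or transplant, does not censor the cardiovascular endpoint where follow-up data exist. Where they do not, censor at the last date on which all components were ascertained.
- **SAP 6.7.8:** add a sensitivity analysis for participants whose post-ESRD data cannot be obtained. One form is to impute their later event times with the hazard multiplied by a stated range of factors, such as 1 to 10, and report how the hazard ratio moves.

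The cost is one question set at contacts sites already owe, a few lines of text and one extra analysis. No new visit or procedure is needed. The downside is record retrieval to confirm self-reported events, probably for a handful of participants.
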